**11.3.1.2 Secondary Endpoints**

1) Definitions

- a) AEs
- b) Clinical laboratory values
- c) Vital signs (blood pressure, pulse rate, and body temperature) and body weight
- d) ECOG PS
- e) Twelve-lead ECG
- f) Chest X-ray

2) Analysis set

Safety analysis set

3) Analysis method

a) Adverse events

The following tabulations will be performed for each cohort:

- All AEs occurring after the start of IMP administration (treatment-emergent adverse events) (all events, SOCs, and PTs) will be summarized using the Medical Dictionary for Regulatory Activities (MedDRA).
- Adverse events will be summarized (number and percentage of subjects with AEs) by CTCAE grade.  
However, if an event occurs more than once in the same subject, the most severe episode will be included in the tabulation.
- Adverse events in treated subjects in each course will be summarized (number and percentage of subjects with AEs) by timing of occurrence.
- Deaths, other SAEs, and AEs leading to discontinuation will be summarized.
- Adverse drug reactions (AEs assessed as related to the IMP) will be summarized in the same manner as AEs.
- Dose-limiting toxicities (including events occurring after the start of Course 2) will be summarized (number and percentage of subjects with DLTs).

b) Clinical laboratory values

Hematological and blood biochemistry data at each timepoint will be summarized by cohort as follows:

- Descriptive statistics of measurements
- Descriptive statistics of change from baseline

- A shift table of the value at the last evaluation and the worst value after the treatment relative to the baseline value by CTCAE grade

Urinalysis data at each timepoint will be summarized by cohort as follows:

- A shift table of the value at the last evaluation and the worst value after the treatment relative to the baseline value by CTCAE grade

- c) Vital signs (blood pressure, pulse rate, and body temperature) and body weight

Vital signs (blood pressure, pulse rate, and body temperature) and body weight at each timepoint will be summarized by cohort as follows:

- Descriptive statistics of measurements
- Descriptive statistics of change from baseline

- d) Eastern Cooperative Oncology Group performance status

Eastern Cooperative Oncology Group PS at each timepoint will be summarized by cohort (the number and percentage of subjects for each score).

- e) Twelve-lead electrocardiogram

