Based on the occurrence of DLTs, the tolerability at the recommended dose for a next phase study will be confirmed in Japanese subjects as well.

The sponsor will review safety data obtained from the previous cohort(s) and judge the transition to the next cohort, including selection of a cohort to proceed to, based on the advice of the Independent Data Monitoring Committee.

If the number of subjects exhibiting DLT within a cohort is $\geq 2/3$ or $\geq 2/6$, then there will be no transition to the next cohort, and the maximum tolerated dose (MTD) will be determined as follows:

$\geq 2/3$ or $\geq 2/6$ subjects with DLT	MTD
In Cohort 1	$< 36 \text{ mg/m}^2$ in 5-day regimen
In Cohort 2	36 mg/m^2 in 5-day regimen
In Cohort 4	60 mg/m^2 in 5-day regimen

If the incidence of DLT does not reach either $\geq 2/3$ or $\geq 2/6$ in any of the cohorts in the table above, the MTD will not be determined in this study. For Cohort 3 (60 mg/m^2 in 10-day regimen), DLT will be evaluated but the MTD of 10-day regimen will not be determined from the incidence of DLT.

The DLT evaluation period will be from the start of administration in Course 1 to the examination scheduled for Day 29 of Course 1. However, for subjects who have postponed the start of IMP administration scheduled for Day 1 of Course 2 (extended treatment period), the DLT evaluation period will last until the start of IMP administration in Course 2.

Subjects will be hospitalized for treatment during Course 1. Subjects will be required to remain hospitalized until the examination scheduled for Day 29 of Course 1 if they complete the trial in Course 1 (until the withdrawal examination if they are withdrawn during Course 1) and until the start of IMP administration in Course 2 if they proceed to the extended treatment period of Course 2 and the subsequent courses.

Dose-limiting toxicity shall be defined as any of the following AEs occurring during Course 1 for which there is a reasonable probability or possibility of a causal relationship with the IMP (being related to the IMP) if it cannot be reasonably explained by underlying disease, intercurrent illness, or concomitant medications. The severity of AEs will be graded in accordance with Common Terminology Criteria for Adverse Events (CTCAE) version 4.0.

- Non-hematologic toxicity of Grade 3 or higher, except for the following:
 - Nausea, vomiting, or diarrhea of Grade 3 that is controllable by optimal therapy

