9.2 Primary Endpoints

DLT is the primary endpoint of this trial.

DLT evaluation analysis set will be used for the analysis.

- DLTs [preferred term (PT)] which observed on course 1 will be tabulated (number of subjects and incidence rate) by DLT criteria and Medical Dictionary for Regulatory Activities (MedDRA) system organ class (SOC) and PT.

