9.3.1 Adverse Events

AEs will be coded using MedDRA version 20.0.

- The number of subjects and incidence will be summarized for all treatment-emergent AEs (TEAEs).
- The number of subjects and incidence will be summarized for all TEAEs by MedDRA SOC and PT.
- The number of subjects and incidence will be summarized for all TEAEs by MedDRA SOC, PT, and CTCAE grade. If a subject experiences the same TEAE 2 or more times, the most severe grade occurrence will be used for the analysis.
- The number of subjects and incidence will be summarized for all TEAEs by the timing of AE occurrence (in course 1, in or after course 2, and overall), MedDRA SOC and PT. AEs which had occurred in Course 1 and continued beyond course 2 will be included in “in or after course 2” category.

- TEAEs that DLTs and correspond to DLTs (preferred term) which were observed in course 1, in or after course 2, and overall will be tabulated (number of subjects and incidence rate). AEs which had occurred in Course 1 and continued beyond course 2 will be included in “in or after course 2” category.

Adverse drug reactions (TEAEs for which a causal relationship with the IMP are suspected adverse reaction) will be summarized in the same manner as above.

9.3.2 Death, Other Serious Adverse Events, CTCAE Grade 3 or above Adverse Events, and Other Significant Adverse Events

The following TEAEs will be summarized in the same manner as in first bullet of [Section 9.3.1 Adverse Events](#). Also the following TEAEs, excluding TEAEs of grade ≥ 3 , will be summarized in the same manner as in second bullet of [Section 9.3.1 Adverse Events](#).

- Serious TEAEs
- TEAEs leading to death
- TEAEs leading to discontinuation in course 1, in or after course 2, and overall
- TEAEs of grade ≥ 3
- TEAEs leading to postponement of the start of the next course
- TEAEs leading to skipping of IMP administration

Adverse drug reactions (TEAEs for which a causal relationship with the IMP are suspected adverse reaction) will be summarized in the same manner as above.

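### The Course 2-onward column of the SAP 9.3.1 AE and DLT period tables mixes carry-over from Course 1 with new onsets, so it overstates later-course occurrence

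*SAP*

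**What the plan says.** Protocol 11.3.1.2 specifies the AE table in one line: "Adverse events in treated subjects in each course will be summarized (number and percentage of subjects with AEs) by timing of occurrence". For DLTs beyond the primary table it says: "Dose-limiting toxicities (including events occurring after the start of Course 2) will be summarized". Neither line has a rule for events that span courses.

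SAP 9.3.1 sets up the TEAE table as number of subjects and incidence "by the timing of AE occurrence (in course 1, in or after course 2, and overall), MedDRA SOC and PT". It then adds that "AEs which had occurred in Course 1 and continued beyond course 2 will be included in" the category for Course 2 onward. The next table covers "TEAEs that DLTs and correspond to DLTs (preferred term) which were observed in course 1, in or after course 2, and overall", and the same sentence follows it. Adverse drug reactions are to be summarized in the same way, so the rule reaches them too.

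SAP Section 13 lists three changes from the protocol: urinalysis categories, the interim analysis and the Kaplan-Meier plots. The carry-over rule is not among them.

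**The concern.** A column headed by timing of occurrence and filled with incidence should hold events that began in that period. Under the SAP rule, the later column holds new onsets plus events that began in Course 1 and had not ended. That is closer to period prevalence, and nothing in the label says so.

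Carry-over is likely to be common. Protocol 1.2.3 and 3.5 expect myelosuppression and infection. Under Protocol 9.2, the unresolved-DLT withdrawal criterion is not met if the DLT improves by one grade within four weeks, so an improved but unresolved DLT can continue into Course 2.

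Cohort 3 is the most exposed. Protocol 6.1 gives a 10-day Course 1, a 10- or 5-day Course 2 and 5-day courses after that. The cohort exists to assess 10-day tolerability. Toxicity that began in the 10-day Course 1 can be displayed in a column that includes 5-day courses, and a reader comparing columns would misplace it.

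**Working it through.** **Texts side by side**

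- The protocol's later-course DLT summary turns on events occurring after Course 2 starts. The SAP's later column also takes events that had already occurred in Course 1.
- SAP Section 3 ties DLTs to the first course: "Dose-limiting toxicity shall be defined as any of the following AEs occurring during Course 1". A Course 1 DLT shown under later courses sits badly with that definition.
- SAP 9.2, the primary analysis, covers DLTs "which observed on course 1 will be tabulated (number of subjects and incidence rate) by DLT criteria" and has no carry-over rule.
- Two points in the SAP sentence are open. Being included in the later category does not say whether the event also stays in the Course 1 column. Continuing beyond Course 2 could mean into Course 2 or past its end.

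**Arithmetic**

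There is no plan figure to reproduce: the SAP sets no significance level and gives no expected event counts. All counts below are assumed, except that *n* = 6 is the largest cohort size in Protocol 3.4.

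For one preferred term, let *n* be subjects dosed in Course 1, *m* those who start Course 2, *a* subjects with Course 1 onset, *k* those of the *a* whose event continues into Course 2, and *b* subjects with new onset later. The *b* subjects are taken as different from the *a* subjects, and the *k* subjects are among the *m*.

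- By onset: Course 1 = *a*/*n*; later = *b*/*m*.
- SAP rule, event counted in both columns: Course 1 = *a*/*n*; later = (*b* + *k*)/*m*.
- SAP rule, event moved: Course 1 = (*a* − *k*)/*n*; later = (*b* + *k*)/*m*.

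The excess in the later column is *k*/*m* under either reading. Only the Course 1 column depends on the reading.

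| *a*, *k*, *b*, *m* | Course 1 by onset | Later by onset | Later, SAP rule | Course 1 if moved |
|---|---|---|---|---|
| 1, 1, 0, 6 | 1/6 (16.7%) | 0/6 (0%) | 1/6 (16.7%) | 0/6 (0%) |
| 1, 1, 0, 4 | 1/6 (16.7%) | 0/4 (0%) | 1/4 (25.0%) | 0/6 (0%) |
| 2, 1, 0, 4 | 2/6 (33.3%) | 0/4 (0%) | 1/4 (25.0%) | 1/6 (16.7%) |
| 2, 2, 0, 4 | 2/6 (33.3%) | 0/4 (0%) | 2/4 (50.0%) | 0/6 (0%) |
| 3, 2, 1, 4 | 3/6 (50.0%) | 1/4 (25.0%) | 3/4 (75.0%) | 1/6 (16.7%) |

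The overall column is *a* + *b* subjects under every reading. SAP 9.3.1 does not state the denominator of the later column. If all 6 dosed subjects were used where *m* = 4, the SAP-rule entries would be 1/6 (16.7%), 1/6 (16.7%), 2/6 (33.3%) and 3/6 (50.0%). They are smaller, but still above the onset-based values of 0/6 in the first three of these cases and 1/6 (16.7%) in the last.

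**The case against.** The best defence is that the rule is stated openly and that prevalence by period is a legitimate summary. It also has a real advantage: it can keep visible a Course 1 event that gets worse in Course 2. A reader might assume that Protocol 8.1.1 already makes such worsening a new AE, so that classifying by onset alone would lose nothing. It does not. Sections 8.1.1 and 8.3.2 do this only for conditions present at consent and for AEs arising between consent and first dose. Under onset-only classification, a Grade 2 event from Course 1 that reached Grade 4 in Course 2 would appear only under Course 1. This part of the defence stands, and the fix has to deal with it.

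A reader might also infer that the rule empties the Course 1 column, or that it makes the DLT period table contradict SAP 9.2. The documents support neither as a fact. Both need the reading in which events are moved, which the text does not establish. The two DLT tables also use different sets (the DLT analysis set in 9.2, the safety analysis set in 9.3), so their counts could differ anyway.

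Protocol Section 11 leaves analytic detail to the SAP, so for AEs in general a convention for spanning events may be detail rather than a change that Section 13 must list. That is arguable. It is weaker for DLTs, where the protocol's wording is explicit about when the event occurs.

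Finally, SAP 9.3.3 gives shift tables of worst grade in each course and by-subject plots of the main blood counts. These partly cover prolonged cytopenias. They do not cover infections, and they do not correct the label on the AE and DLT tables.

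**Conclusion.** The point holds as a secondary safety-reporting fault. The later column of the TEAE, adverse drug reaction and DLT period tables overstates occurrence from Course 2 onward, contrary to Protocol 11.3.1.2. It does so for any term where at least one subject has a qualifying carried-over event and no new onset of that term. The direction follows from the stated rule under either reading of the Course 1 column. If continuing beyond Course 2 means past its end, fewer events qualify, but those that do still inflate the column.

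The size cannot be fixed from the documents. In the assumed cases with no new later onset and subjects starting Course 2 as denominator, the later column shows 16.7% to 50.0% against 0% by onset. These are illustrations, not forecasts. Understatement of Course 1 is possible but not established.

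A reader might take this further and doubt the tolerability conclusion. The documents do not support that: the primary DLT table in SAP 9.2 carries no such rule, and the escalation and MTD rules do not use the 9.3.1 tables.

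**What to change.** Replace the two carry-over sentences in SAP 9.3.1 with four rules.

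1. Assign each TEAE and DLT to a period by onset date, with subjects dosed in that period as denominator. Onset dates are collected under Protocol 8.3.2, and SAP 9.1 already tabulates subjects dosed per course.
2. Show Course 1 events still ongoing at the start of Course 2 on a separate, labelled line. This also removes the ambiguity about continuing beyond Course 2.
3. Count a Course 1 event whose CTCAE grade worsens in or after Course 2 in the later period too, or on its own line. Confirm that the CRF dates such worsening, because Protocol 8.3.2 provides an exacerbation date only for the two cases described above.
4. Apply the same rules to adverse drug reactions.

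If the sponsor prefers the present rule, the tables should be relabelled as prevalence by period, the text should say whether carried-over events also count under Course 1, the denominators should be stated, and the rule should be listed in SAP Section 13.

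The cost is a small programming change and one extra table line, plus the check in rule 3.

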9.3.3 Clinical Laboratory Tests

The following items will be tabulated by cohort and overall (Cohorts 1, 2, and 4) for hematological and biochemical tests performed at each time point.

- Descriptive statistics of the measured values
- Descriptive statistics of the change from baseline
- Shift tables comparing the baseline grade with last grade, worst grade through all courses and worst grade of each course categorized by CTCAE grade
- Shift tables comparing the baseline values with last value, worst value through all courses and worst value of each course by using the normality judgment (high, normal, low)

If the laboratory test parameter has both upper limit of normal and lower limit of normal, larger difference one from median of normal range will be taken as worst value.

The following item will be tabulated by cohort and overall (Cohorts 1, 2, and 4) for the urinalysis.

- Shift tables comparing the baseline values with last value, worst value through all courses and worst value of each course.

Also, some of laboratory test parameter will be figured by subject performed at each time point of course 1 and all courses.

- Line plots will be used to assess hemoglobin, red blood cell, white blood cell, neutrophil, lymphocytes and platelet.

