### **3.2 Rationale for Trial Design**

In the trial, the dose escalation was planned with consideration of the subjects' safety and based on the "Guidelines for Clinical Evaluation of Antimalignant Tumor Drugs (Notification No. 1101001 of the Evaluation and Licensing Division, Pharmaceutical and Food Safety Bureau dated 01 Nov 2005)."

As mentioned in [Section 1.2.3](#) Trial Rationale, the doses and regimen were chosen based on evaluations of the safety, efficacy, and PD of SGI-110 in a clinical trial conducted outside of Japan (Study SGI-110-01), and it has been decided to adopt a study design to evaluate the tolerability in each cohort and gradually escalate the dose.

Since results of Study SGI-110-01 suggest that the recommended dose for non-Japanese patients is assumed to be 60 mg/m^2, the primary dose to be investigated has been set as 60 mg/m^2. This study is the first clinical trial of SGI-110 involving Japanese patients with AML and, therefore, in considering the subjects' safety, the initial dose will be 36 mg/m^2, which was one of the doses used in Study SGI-110-01 and is a lower dose than the primary dose of 60 mg/m^2. The maximum dose will be 90 mg/m^2, which was determined to be the MTD in Study SGI-110-01 and is suggested to be effective according to exploratory evaluation. In addition, the tolerability of SGI-110 at 60 mg/m^2 once daily for 10 days will be evaluated in Japanese patients in this study because the same dose and regimen is planned to be adopted in Study SGI-110-06 in patients with relapsed or refractory AML.

As mentioned in [Section 1.2.2](#) Clinical Study Results, occurrences of myelosuppression and decreased blood cell counts, and infections attributable to these, as well as

occurrences of digestive symptoms are anticipated following administration of SGI-110. Therefore subjects will be hospitalized during Course 1, when the IMP will be administered for the first time to them, so they can be carefully monitored. Thereafter, the subjects are to visit the trial site at least once weekly to undergo hematological tests for evaluation of decreased blood cell counts and to undergo a medical examination by a physician to check their general condition. In addition, a chest X-ray examination and blood biochemistry test are to be performed before the start of the next course in order to ensure the subjects' safety.

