### **6.2.2 Restricted Concomitant Drugs and Therapies**

Any drug or therapy that is not prohibited, as specified above, can be administered during the trial.

The investigator or subinvestigator should administer blood transfusions for supportive care as appropriate. Prophylactic medications should be provided if necessary in order to prevent bacterial, fungal, viral, and opportunistic infections and deaths from these

infections. Antibiotics and other drugs can be given to prevent and control febrile neutropenia. In the trial, febrile neutropenia is defined as a neutrophil count below 500/ $\mu$ L and body temperature of 38°C or higher.

Subjects with fever will undergo physical examination and peripheral blood tests (including differential leukocyte count and blood culture). Subjects who have been confirmed to have febrile neutropenia or sepsis (including suspected cases) by physical examination will be hospitalized and properly treated with a broad-spectrum antibiotic and other medication. The package insert should be observed for use of hematopoietic growth factors such as a granulocyte-colony stimulating factor.

When any drugs other than the IMP (excluding physiological saline and dextrose solution used for reconstitution) have been used from 28 days before the start of IMP administration until the date of withdrawal from the trial, the name of the drug, purpose of use, regimen, daily dose, route of administration, and start and end dates of treatment will be recorded in the case report form (CRF) (or in the medical records during the extended treatment part). If blood transfusion has been performed, the type, purpose, volume, and date of blood transfusion will be recorded in the CRF (or in the medical records during the extended treatment part). For treatments other than medication and blood transfusion, the name, purpose, and start and end dates of the therapy will be recorded in the CRF (or in the medical records during the extended treatment part).

[Rationales for prohibited concomitant drugs and therapies]

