9.3.5 ECG (12-Lead ECG)

Electrocardiographic (ECG) assessment by site investigator will be used for the analysis.

The following items will be tabulated for heart rate, PR interval, RR interval, QRS interval, QT interval, and QT interval as corrected by Fridericia's formula (QTcF interval) at each time point.

- Descriptive statistics of the measured values
- Descriptive statistics of the change from baseline

The number of subjects and incidence of the following items will be tabulated by cohort for QTcF interval of last value and worst value (maximum value obtained after the start of IMP administration).

- Measured values will be classified as "greater than 450 ms", "greater than 480 ms", and "greater than 500 ms" for tabulation.
- Changes from baseline will be classified as "greater than 30 ms" and "greater than 60 ms" for tabulation.

The following item will be tabulated by cohort using the normality judgment (normal or abnormal) for the electrocardiogram at each time point.

- Shift table from baseline

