11.1 DNA Methylation Inhibition

The following analysis will be conducted by cohort and overall (Cohorts 1, 2, and 4) for the subjects with the measurement of the degree of DNA methylation inhibition of LINE-1.

- Descriptive statistics of the DNA LINE-1 demethylation (defined as percent change from baseline in methylation value) at each time point. Also, line plots will be used to assess DNA LINE-1 demethylation [Mean \pm Standard deviation (SD)] at each time point.
- Summary of the maximum DNA LINE-1 demethylation (defined as the largest percent decrease from baseline in methylation values within a subject between Day 8 and Day 29 of the first treatment course) using the descriptive statistics. Also, bar charts will be used to assess the maximum DNA LINE-1 demethylation within a subject between Day 8 and Day 29 of the first treatment course.
- Line plots of DNA LINE-1 demethylation will be produced for responders, non-responders, and overall in the pharmacodynamics analyses set. Responders will be defined as those subjects who meet the criteria of overall remission.

12 Rationale for Target Number of Subjects

For Cohorts 1, 2, and 4, tolerability will be evaluated in at least 3 subjects per cohort based on the Guidelines for Clinical Evaluation of Antimalignant Tumor Drugs. If DLTs are evaluated in 3 subjects in a cohort for the recommended dose and regimen, additional subjects will be enrolled for further safety evaluation in 6 subjects. For Cohort 3, tolerability will be evaluated in 6 subjects.

13 Changes From Analyses Planned in the Protocol

Categorization of urinalysis in shift tables was changed from CTCAE grade to qualitative value.

One interim analysis for cohort 1, 2 and 4 of this study will take place that the data will be locked on 25Aug2017.

Kaplan-Meier plots of overall survival with median survival time will be produced regardless of number of subjects in each cohort.

14 References

¹ Cheson BD, Bennett JM, Kopecky KJ, Büchner T, Willman CL, Estey EH, et al. Revised recommendations of the International Working Group for Diagnosis, Standardization of Response Criteria, Treatment Outcomes, and Reporting Standards for Therapeutic Trials in Acute Myeloid Leukemia. *J Clin Oncol*. 2003 Dec 15;21(24):4642-9.

² NCCN Guidelines: Acute Myeloid Leukemia. Version 2.2014. NCCN.org.

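### For laboratory tests with two limits, the SAP's single worst value ignores direction, so a deep low value can be tabulated as high

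*SAP*

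**What the plan says.** SAP 9.3.3 plans two kinds of shift table for hematology and biochemistry. One compares baseline with the last and worst CTCAE grade. The other compares baseline with the last value, the worst value through all courses and the "worst value of each course by using the normality judgment (high, normal, low").

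A selection rule follows. "If the laboratory test parameter has both upper limit of normal and lower limit of normal", the "larger difference one from median of normal range will be taken as worst value". The rule names no direction and does not itself say that only post-dose values count.

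Three other places bear on it:

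- SAP 9.3.5 defines the extreme QTcF with both a direction and a time limit: "worst value (maximum value obtained after the start of IMP administration").
- Protocol 11.3.1.2 plans the hematology and biochemistry shift table on the last value and "the worst value after the treatment relative to the baseline value by CTCAE grade". It has no high/normal/low table and no distance rule.
- SAP Section 13 records one shift-table change, "Categorization of urinalysis in shift tables was changed from CTCAE grade to qualitative value", but not the added high/normal/low table.

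**The concern.** A test with two limits can be abnormal in two opposite ways, and a single worst value has to discard one of them. The SAP discards whichever lies nearer the middle of the normal range. For blood counts this is lopsided: a count cannot fall below zero, so its low-side distance is at most the midpoint, while its high-side distance has no ceiling. The rule therefore leans towards high.

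That is the wrong lean for this drug. Protocol 3.2 anticipates "occurrences of myelosuppression and decreased blood cell counts". A subject with a deep nadir and a large enough high value in the same period would be counted as high and would be missing from the low column. If that subject's baseline was also high, the table would show no shift at all.

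Both extremes can fall in one course. Hematology is scheduled on Days 8, 15, 22 and 29 of Course 1 (Protocol 7.1.4.1.3, 7.1.4.1.4, 7.1.4.2.3 and 7.1.4.2.4), and Protocol 6.2.2 allows for "use of hematopoietic growth factors such as a granulocyte-colony stimulating factor". SAP 8.1 also provides a baseline leukocyte category of 20.0 × 10⁹/L or more, and the eligibility criteria set no white-cell ceiling, so some subjects may start high and fall later. Neither fact establishes how often the problem will arise.

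**Working it through.** The plan states no figure here, so there is none to reproduce. The check applies the SAP 9.3.3 rule directly.

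**Inputs.** The rule is from SAP 9.3.3. I read the median of the normal range as its midpoint. The reference ranges and example values are my assumptions, because the documents give none; two ranges are shown per test.

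**Formula.** Let the limits be L and U, with m = (L + U)/2.

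- A low value v deviates by m − v; a high value H deviates by H − m.
- H is selected when H − m > m − v, that is, when H > L + U − v.
- With v = 0 the threshold is L + U. Above it, no count, however low, can be selected.
- An in-range value never displaces an out-of-range one, since in-range values lie within (U − L)/2 of m and out-of-range values lie farther away. The loss is always low hidden by high, or high hidden by low.

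**Thresholds, L + U − v**

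| Test | Low value v | First assumed range | H must exceed | Second assumed range | H must exceed |
|---|---|---|---|---|---|
| WBC (10⁹/L) | 0.5 | 3.3–8.6 | 11.9 − 0.5 = 11.4 | 4–10 | 14.0 − 0.5 = 13.5 |
| WBC (10⁹/L) | 0 | 3.3–8.6 | 11.9 | 4–10 | 14.0 |
| Neutrophils (10⁹/L) | 0.2 | 1.5–7.0 | 8.5 − 0.2 = 8.3 | 2.0–7.5 | 9.5 − 0.2 = 9.3 |
| Lymphocytes (10⁹/L) | 0.2 | 1.0–3.5 | 4.5 − 0.2 = 4.3 | 1.0–4.0 | 5.0 − 0.2 = 4.8 |
| Potassium (mmol/L) | 2.8 | 3.5–5.0 | 8.5 − 2.8 = 5.7 | 3.6–4.8 | 8.4 − 2.8 = 5.6 |
| Platelets (10⁹/L) | 8 | 150–350 | 500 − 8 = 492 | 150–450 | 600 − 8 = 592 |
| Hemoglobin (g/dL) | 6 | 11.5–15 | 26.5 − 6 = 20.5 | 13.5–17 | 30.5 − 6 = 24.5 |

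**Worked series.** Take post-dose WBC on Days 8, 15, 22 and 29 of Course 1.

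- Series 15, 3, 0.5, 0.8. Under 3.3–8.6 (m = 5.95), 15 deviates by 9.05 and 0.5 by 5.45. Under 4–10 (m = 7.0), the deviations are 8.0 and 6.5. The subject is classified high under both ranges.
- Replace 15 by 13. The deviations are 7.05 against 5.45 (high) and 6.0 against 6.5 (low), so the answer depends on the range.
- Replace 15 by 10. The deviations are 4.05 against 5.45 and 3.0 against 6.5. The subject is classified low under both ranges. Under the first range the 10 is itself high, and is now the value lost.

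**Scope.** The rule works within each tabulated period. A high value in one course cannot alter another course's entry, but the all-courses entry pools every course and so gives more room for both extremes.

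**The case against.** The strongest case against is that little depends on this table. It carries no severity: a mild and a profound low value look the same in it even when correctly classified. Severity is in the CTCAE-grade table, which is worded in terms of worst grade rather than worst value. Low counts also appear in the per-visit statistics, the by-subject line plots of six blood counts, and the AE and DLT tables. The trial has at most 24 subjects and no tests or intervals. The reference ranges are assumed. The protocol does not say whether differential cells are reported as percentages or absolute counts, so the neutrophil and lymphocyte rows are uncertain. Displacement is most plausible for total white cells, which are not a DLT criterion. Post-baseline is the natural reading of a worst value set against baseline. QTcF is tabulated only for prolongation, so it needs no two-sided rule. SAP Section 13 also omits other added displays, such as responder survival curves.

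Most of this stands as a limit on consequence. The post-baseline reading is probably intended, though the sentence should say so, because Course 1 includes a pre-dose hematology sample on Day 1. The Section 13 omission is secondary.

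None of it repairs the table. The six plots include no chemistry test, and per-visit statistics do not show a subject's worst shift. The SAP also does not say how the worst grade is chosen where both directions are graded.

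**Conclusion.** The concern holds: the rule is wrong as written. The inequality H > L + U − v follows from the SAP sentence alone, once the median of the range is read as its midpoint. Its practical reach depends on assumed ranges and example values: plausible for white cells, possible for neutrophils (if reported as two-limit absolute counts), lymphocytes (likewise) and two-sided chemistry tests, and remote for platelets and hemoglobin. The documents do not allow a frequency to be estimated.

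The damage is confined to the high/normal/low shift table, provided the sentence does not also select the value that is graded, which the SAP leaves unsaid. DLT evaluation and dose decisions are not touched. It should be corrected because it can misclassify subjects in the direction opposite to the expected toxicity.

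**What to change.** Replace the sentence in SAP 9.3.3. For every parameter with both limits, derive the lowest and the highest post-baseline value separately, through all courses and within each course, and give a high/normal/low shift table for each. State that the worst CTCAE grade is the highest post-baseline grade, taken by direction where both directions are graded. List the added high/normal/low table in SAP Section 13.

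The cost is SAP wording and one further shift table per two-sided parameter. No new data are needed.

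In the series 15, 3, 0.5, 0.8, the subject would then appear once as low (0.5) and once as high (15), so neither finding is lost.
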